1.3. Exemption Number

1 2 3 4 5 6 7 8

1.4. * Clinical Trial Questionnaire

If the answers to all four questions below are yes, this study meets the definition of a Clinical Trial.

1.4.a. Does the study involve human participants?

Yes No

1.4.b. Are the participants prospectively assigned to an intervention?

Yes No

1.4.c. Is the study designed to evaluate the effect of the intervention on the participants?

Yes No

1.4.d. Is the effect that will be evaluated a health-related biomedical or behavioral outcome?

Yes No

1.5. Provide the ClinicalTrials.gov Identifier (e.g., NCT87654321) for this trial, if applicable

Section 2 - Study Population Characteristics

2.1. Conditions or Focus of Study

Language Development Disorders

2.2. Eligibility Criteria

Inclusionary Criteria

All participating children must meet the following inclusionary criteria:

- between the ages of 4 and 6 years of age;
- English monolingual;
- present with phonological disorder (PD, n = 12), developmental language disorder (DLD, n = 6), or co-occurring PD-DLD (n = 18) (see below for additional criteria for inclusion).

Participants will complete a battery of assessment measures. Information gleaned from these measures will be used to further determine eligibility for the proposed study, which include both quantitative and qualitative criteria.

In addition, all PD and PD-DLD participants must:

- exhibit 5 or more sounds in error across three or more speech sound manner classes,
- score less than or equal to 1.5 standard deviations below the mean on the Goldman-Fristoe Test of Articulation 3 (GFTA3), [135] and
- exhibit less than or equal to 20% accuracy on final consonants and clusters independent of tense morphemes.

Moreover, all DLD and PD-DLD participants must:

- score less than or equal to 1 standard deviation below the mean on the Preschool Language Scales - Fourth Edition (PLS-4), [136] a test of expressive and receptive language; and
- exhibit a mean length of utterance (MLU) less than or equal to 1 standard deviation below the mean for age- and demographic-matched peers, based on a language sample. [4]

Exclusionary Criteria

All participants must:

- not be receiving speech/language services elsewhere,
- pass a binaural hearing screening at 20dB,
- achieve score above a standard score of 70 on a test of nonverbal cognition (Leiter-R) [137], and
- have typical intellectual, hearing, social-emotional, and neurological development, per parent report.

In addition, to rule out concomitant difficulty in other domains of language all PD participants must:

- score > 1 standard deviation below the mean on the PLS-4 [136]
- have an MLU > 1 standard deviation below the mean for age- and demographic-matched peers, based on a language sample [4]

To rule out concomitant difficulty in phonology, the DLD participants must:

- score > 1.5 standard deviations below the mean on the GFTA3, [135] and
- exhibit fewer than 5 sounds in error and > 20% accuracy on final consonants and clusters independent of tense morphemes.

If the above criteria are not met, a child will be excluded from participation.

2.3. Age Limits

Minimum Age

4

Years

Maximum Age

6

Years

2.4. Inclusion of Women, Minorities, and Children

Inclusion of women, n

2.5. Recruitment and Retention Plan

RECRUITMENT_PLAN

2.6. Recruitment Status

Not yet recruiting

2.7. Study Timeline

STUDY TIMELINE_Ba

Delete Attachment

**2.8. Enrollment of First Subject**

01-May-2019

Anticipated

Inclusion Enrollment Report(s)

Add Inclusion Enrollment Report

Remove Inclusion Enrollment Report

Section 3 - Protection and Monitoring Plans**3.1. Protection of Human Subjects**

PROTECTION OF HU

Delete Attachment

**3.2. Is this a multi-site study that will use the same protocol to conduct non-exempt human subjects research at more than one domestic site?** Yes No N/A**If yes, describe the single IRB plan**

Add Attachment

3.3. Data and Safety Monitoring Plan

DATA _ SAFETY MON

Delete Attachment

**3.4. Will a Data and Safety Monitoring Board be appointed for this study?** Yes No**3.5. Overall Structure of the Study Team**

OVERALL STRUCTURE

Delete Attachment

**Section 4 - Protocol Synopsis****4.1. Brief Summary**

This proposed research program will evaluate the influence of morpho-phonological interaction in the language of children with phonological disorder (PD), those with developmental language disorder (DLD), and those children with co-occurring PD and DLD (PD-DLD) through manipulation of phonological and morphological complexity in the selection of treatment target words. Experiment 1

4.2. Study Design**4.2.a. Narrative Study Description**

This proposed research program will evaluate the influence of morpho-phonological interaction in the language of children with phonological disorder (PD), those with developmental language disorder (DLD), and those children with co-occurring PD and DLD (PD-DLD) through manipulation of phonological and morphological complexity in the selection of treatment target words. Experiment 1

4.2.b. Primary Purpose

Treatment

4.2.c. Interventions

Intervention Type	Behavioral (e.g., Psychotherapy, Lifestyle Counseling)	
Name	Language Intervention	
Description	The clinician will provide models, verbal and/or tactile cues, and/or conversational recasts of targeted linguistic forms (consonants, consonant clusters, morphemes) following the methodology of Gierut and colleagues (Experiment 1) and of Plante and colleagues (Experiment 2). A minimum of 50 (Experiment 2) and up to 100 (Experiment 1) productions will be targeted per 1-hour session.	

4.2.d. Study Phase

Phase 3

Is this an NIH-defined Phase III clinical trial? Yes No**4.2.e. Intervention Model**

Parallel

4.2.f. Masking Yes No Participant Care Provider Investigator Outcomes Assessor**4.2.g. Allocation**

Non-randomized

4.3. Outcome Measures

Name	Treatment Probe	
Type	Primary	
Time Frame	All participants will complete the Treatment Probe at the start of each treatment session. Maximum 18 sessions.	
Description	The Treatment Probe is made of the selected treatment stimuli (verbs) that are consistent with the child's assigned experimental condition. These verbs have a final consonant or consonant clusters ("sees" vs. "seats"), and are mono- or bi-morphemic ("tease" vs. "sees"). Children will be asked to pronounce each word following presentation of a corresponding picture and a verbal prompt. The Treatment Probe allows us to track the effectiveness of treatment on the treated stimuli.	
Name	Generalization Probe	
Type	Primary	

Time Frame	All participants will complete the Generalization Probe during baseline phase (minimum 3 times), after 9 treatment sessions, after the last treatment session, and 2 weeks post-treatment.
Description	The Generalization Probe consists of words and phrases that target each consonant, cluster, and morpho-syntactic constructs a minimum of 10 times across relevant contexts (i.e., word- and utterance-position). The Generalization Probe allows us to track the effects of treatment (generalization) to untreated stimuli and to monitor control variables.

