condition). PD-DLD children will be assigned to one of four conditions of Experiment 1 (n=3 per condition) or one of two conditions of Experiment 2 (n=3 per condition). Following treatment condition assignment, specific treatment target verb stimuli will be identified for each child.

The next set of procedures involve the following, with 1-hour sessions occurring three times weekly (see also C.2.2. *Experimental design*):

- Baseline testing phase, to include administration of the Generalization Probe (a minimum of three baseline sessions per child);
- Treatment phase (maximum 18 sessions), to include
 - Treatment Probe administered at the start of each session and
 - Generalization Probe collected after 9 treatment sessions;
- Post-treatment testing phase, to include Generalization Probe collected immediately following treatment, and at 2 weeks and 2 months posttreatment.

Following completion of the post-treatment testing, children will be dismissed from participation in the research program. Referrals, if needed, for further speech/language services will be provided.

The risks of the procedures associated with the proposed project are minimal and typical of children receiving speech/language services in the schools, with the exception that there is more testing involved, treatment occurs more frequently (three times per week as compared to 1 to 2 times per week in a typical school setting), and the procedures will occur at the university clinic. No individual testing or treatment session will last longer than 1 hour. Risks to the children may include boredom or fatigue. The children will also be informed that they can take breaks or permanently end any session.

Additionally, the frequent visits to the university for participation in the study may incur costs to participants' caregivers in terms of their time and transportation. For that reason, we will offer incentives for participation in the study.

2. Adequacy of Protection Against Risk

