The IRB presumes the PI is implementing protocol procedures consistent with IRB approval. However, the IRB recognizes that deviations and exceptions to approved IRB protocols may occur. A protocol deviation occurs when there is inconsistency between the procedures carried out in a study and the procedures stated in the research protocol, or when regulations regarding the manner in which research is being conducted are not being followed. Protocol deviations may directly harm or present the risk of harm to human subjects, or may be administrative in nature, such as those related to data or record keeping. As indicated in section XI, protocol deviations should be reported to the IRB.

STATISTICAL DESIGN AND POWER

This study employs a single-subject, staggered, multiple-baseline design.^{82,117-119} Consistent with this design, it includes a standard (minimum) number of subjects per study condition (n=3). Experiment 1 includes four different treatment conditions and two populations, and thus includes 24 participants (3 participants x 4 conditions x 2 populations). Experiment 2 includes two different treatment conditions and two populations, and thus includes 12 participants (3 participants x 2 conditions x 2 populations).

Consistent with the staggered MBL design, analyses will focus on individual performance. We will complete a visual inspection of accuracy data plotted over time for each child.^{116,118,132} Level, slope, and variability of accuracy scores across all data points will be evaluated within and across children to compare different legs of the multiple baseline within and across treatment conditions for each experiment.^{118,119,133} This type of individual case data allows us to examine individual differences in performance during and following treatment and is particularly meaningful to practicing speech-language pathologists.

In addition, clinically meaningful effect size will be determined by calculating the difference in mean accuracy across pretreatment probes and mean accuracy posttreatment divided by the standard deviation of accuracy post-treatment on the Generalization Probe.^{73,116} Effect sizes obtained for each treatment condition in each experiment will be compared relative to one another, and to results from published studies reporting effect size.

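### The Treatment Probe, one of two primary outcomes, is scheduled only at treatment sessions, so the treated words have one pre-teaching point and no repeated baseline.

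*Combined protocol and SAP*

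**What the plan says.** Section 4.3 (Outcome Measures) names two primary outcomes. For the Treatment Probe, which is built from each child's own treatment verbs and is meant to show how well treatment works on them, the time frame reads "All participants will complete the Treatment Probe at the start of each treatment session", with a maximum of 18 sessions. The Generalization Probe covers untreated items and control variables. Section 4.3 places it at baseline (at least three times), after 9 sessions, after the last session and 2 weeks later.

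The Protection of Human Subjects attachment, part 1.b, gives the same picture by phase:

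- Baseline: "Baseline testing phase, to include administration of the Generalization Probe (a minimum of three baseline sessions per child".
- Treatment: "Treatment Probe administered at the start of each session", plus one Generalization Probe after 9 sessions.
- Post-treatment: "Generalization Probe collected immediately following treatment, and at 2 weeks and 2 months posttreatment".

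On the order of steps, part 1.b says "Following treatment condition assignment, specific treatment target verb stimuli will be identified for each child", and then "The next set of procedures involve the following, with 1-hour sessions occurring three times weekly". The list that follows starts with baseline testing.

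The Statistical Design and Power attachment describes a single-subject, staggered multiple-baseline design. It says "We will complete a visual inspection of accuracy data plotted over time for each child" and, on comparing the staggered starts, "Level, slope, and variability of accuracy scores across all data points will be evaluated within and across children to compare different legs". Neither sentence names a probe. Only the effect size is tied to one, the Generalization Probe.

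**The concern.** In a staggered multiple-baseline design, control comes from measuring the later legs repeatedly, while still untreated, as the earlier legs are being taught. For the treated words no leg has such a series. A single pre-teaching point gives a level but no slope and no variability. Read alone, a rise in Treatment Probe accuracy over sessions cannot be separated from maturation, repeated testing or a trend already under way in those words.

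This matters because the study's manipulation lies in the choice of treatment words (section 4.1), and the Treatment Probe is the primary outcome that measures those words. Other safeguards are few: allocation is non-randomized (section 4.2.g), each condition has three children per population, and no untreated group is described. Baseline points cannot be recovered once teaching has started, so the choice has to be made beforehand. Section 2.6 lists the study as not yet recruiting.

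**Working it through.** **The plan's own sample size.** Experiment 1: 3 children x 4 conditions x 2 populations = 24. Experiment 2: 3 x 2 x 2 = 12. Total 24 + 12 = 36, as stated. Condition-by-population sets: (4 x 2) + (2 x 2) = 8 + 4 = 12, with 3 children in each.

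**Probe points per child**, counted from section 4.3 and part 1.b, for a child who uses the maximum 18 sessions:

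| Phase | Treatment Probe | Generalization Probe |
|---|---|---|
| Baseline | 0 | at least 3 |
| Start of session 1, before teaching | 1 | 0 |
| After teaching begins | 18 - 1 = 17 | 1 (after 9 sessions) |
| Post-treatment | 0 | 2 (section 4.3) or 3 (part 1.b, which adds 2 months) |
| Total | 18 | at least 6 or 7 |

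**What those points can support.** With k points in a phase, a standard deviation has k - 1 degrees of freedom and a fitted slope leaves k - 2.

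- Treatment Probe before teaching, k = 1: 0 degrees of freedom for the standard deviation, and a slope cannot be fitted.
- Generalization Probe at baseline, k = 3: 2 and 1, so level, slope and variability can be described, if coarsely.
- Generalization Probe during treatment, k = 1: no treatment-phase slope. At three sessions a week the point falls at 9 / 3 = 3 weeks, so the timing of onset is coarse.

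The stagger does not change the first line. The plan does not give baseline lengths. If they were 3/4/5 or 3/5/7 sessions within a set (assumed), every leg would still have no baseline-phase Treatment Probe point.

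**If the Treatment Probe were added** at the minimum three baseline sessions and the immediate post-treatment visit:

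- Pre-teaching points per child: 3 + 1 = 4, which gives 3 and 2 degrees of freedom.
- Added baseline probes: 3 x 3 = 9 per set; 9 x 12 = 108.
- Added post-treatment probes: 36. Total 108 + 36 = 144, or 4 per child.
- Double coding under the 20% rule in the Data and Safety Monitoring Plan: 0.20 x 144 = 28.8, about 29 probes.
- With the assumed stagger: (3 + 4 + 5) x 12 + 36 = 180, up to (3 + 5 + 7) x 12 + 36 = 216.

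**The case against.** The strongest reply is that the Generalization Probe carries the design. It has at least three baseline points, covers each consonant, cluster and morpho-syntactic construct at least 10 times, and includes control variables in which general maturation or practice should also show. Section 4.2.c describes the teaching target as linguistic forms, and those forms do have a baseline. This stands. A reader might infer that the planned leg comparison has no baseline at all, or that the design fails as a whole. The documents do not support that, because the statistical section never assigns the leg comparison to the Treatment Probe. It does not assign it to the Generalization Probe either, and that is what needs settling.

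A reader might also infer that the treated words have no control of any kind. That goes too far. A later-leg child's session-1 probe follows a longer untreated period than an earlier-leg child's, which is a weak between-child check: one point per child, three children per set, and verbs identified separately for each child. In addition, PD and PD-DLD children (12 + 18 = 30 of 36) must enter with 20% or less accuracy on final consonants and clusters, which limits their starting level. But that is a screening result independent of tense morphemes, not a repeated measure of the chosen verbs. The 6 DLD-only children must be above 20%.

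Finally, the document may be incomplete on this point. Part 1.b refers to a section C.2.2 that is not included, the narratives in sections 4.1 and 4.2.a break off at Experiment 1, and the phase lists are not worded as exhaustive. The reliability rule lists baseline data separately from generalization data, which may hint at another baseline measure but names none. So it cannot be said that treated words will never be probed at baseline, only that the available text does not schedule it.

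**Conclusion.** The point holds in a limited form. As scheduled, each child has one pre-teaching Treatment Probe point, no baseline-phase points and no post-treatment points. The up to 18 points can describe the course during treatment, but they cannot by themselves support a baseline-to-treatment comparison for the treated words. The Generalization Probe supports a baseline contrast for the targeted forms in untreated items, and its control items and the entry criterion give partial protection. The gap therefore concerns conclusions about the treated words, not the study as a whole.

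It should be fixed before recruitment, because it affects what can be concluded from a primary outcome and the remedy is cheap. Confidence is medium: the finding assumes that section C.2.2 does not already schedule baseline Treatment Probes.

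**What to change.** Choose one of two routes.

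(a) In section 4.3 and part 1.b, add the Treatment Probe at each existing baseline session (minimum three) and at the immediate post-treatment visit. This is feasible because each child's verbs are identified before baseline begins. In the statistical section, name this series as the basis for leg comparisons on treated words. The cost is at least 4 short picture-naming probes per child, 144 in all (180 to 216 under the assumed stagger), with about 29 double-coded at the minimum. They use visits already planned and no new instrument. There are two downsides: added time within sessions capped at 1 hour (probe length is not stated), and extra untaught exposure to the treated words, greater in later legs.

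(b) Leave the schedule alone and state in the statistical section that leg comparisons and causal conclusions rest on the Generalization Probe, that the Treatment Probe is descriptive, and that no treatment-phase slope is claimed from the single mid-treatment Generalization Probe. This is a text change with no added testing.

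If section C.2.2 already schedules baseline Treatment Probes, carry that schedule into section 4.3 and part 1.b, and name the probe for each comparison in the statistical section.

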4.4. Statistical Design and Power

STATISTICAL DESIGN

Delete Attachment

4.5. Subject Participation Duration

6 months

4.6. Will the study use an FDA-regulated intervention?

Yes No

4.6.a. If yes, describe the availability of Investigational Product (IP) and Investigational New Drug (IND)/Investigational Device Exemption (IDE) status

Add Attachment

4.7. Dissemination Plan

DISSEMINATION PLAN

Delete Attachment

Section 5 - Other Clinical Trial-related Attachments

5.1. Other Clinical Trial-related Attachments

Add Attachment

Inclusion Enrollment Report

1. * Using an Existing Dataset or Resource Yes No

2. * Enrollment Location Type Domestic Foreign

3. Enrollment Country(ies)

USA: UNITED STATES Delete

4. Enrollment Location(s)

San Diego, CA

5. Comments

(This field is currently empty.)

Planned

Racial Categories	Ethnic Categories					
	Not Hispanic or Latino		Hispanic or Latino			
	Female	Male	Female	Male		
American Indian/Alaska Native	1	1	1	1	4	
Asian	1	1	0	0	2	
Native Hawaiian or Other Pacific Islander	1	1	0	0	2	
Black or African American	1	1	0	0	2	
White	7	7	3	3	20	
More than One Race	3	3	2	2	10	
Total	14	14	6	6	40	

Cumulative (Actual)

Racial Categories	Ethnic Categories										
	Not Hispanic or Latino			Hispanic or Latino			Unknown/Not Reported Ethnicity				
	Female	Male	Unknown/Not Reported	Female	Male	Unknown/Not Reported	Female	Male	Unknown/Not Reported		
American Indian/Alaska Native											
Asian											
Native Hawaiian or Other Pacific Islander											
Black or African American											
White											
More than One Race											
Unknown or Not Reported											
Total											

[< Previous Report](#)

Report 1 of 1

[Next Report >](#)

[|<< First Report](#)

[Delete Report](#)

[Last Report >>|](#)

INCLUSION OF WOMEN AND MINORITIES

Both male and female children will be recruited equally for this study. We expect that there will be an equal number of female and male participants within each group, as prevalence of PD, DLD, and PD-DLD is roughly comparable across females and males insofar as the number of participants that we plan to recruit is concerned.^{138,139}

Phonological disorder and developmental language disorder affect individuals of all racial and ethnic backgrounds.¹⁴⁰ We do not exclude based on these criteria. Given the diversity of San Diego County, and in particular San Diego Unified School District, we are able to obtain participants from all ethnic groups. We will not exclude any participant on the basis of race or ethnicity.

INCLUSION OF CHILDREN

All participants will be children, ages 4 to 6 years. This age range represents a key time in language development and diagnosis of phonological disorder (PD) and developmental language disorder (DLD). The PI ([name]) has conducted various treatment studies for children with PD. The Co-PI ([name]) is a clinically certified speech-language pathologist, specializing in enhancing clinical assessment, particularly for children with DLD. As such, the PI, Co-PI, and the research team have extensive experience conducting standardized and non-standardized language testing of children in this age range. In addition, all personnel working on this project have completed training in the protection of human subjects. The data will be collected within the labs and the university clinic that serve children and include facilities capable of accommodating children. The recruitment sites identified within San Diego Unified School District are sufficient to provide the targeted number of participants.

RECRUITMENT AND RETENTION PLAN

Recruitment:

The participants will be recruited through schools and community organizations but will not be enrolled in any other speech/language services elsewhere. Both male and female participants will be recruited, as will children from varied racial/ethnic backgrounds.

Participants will be recruited through long-standing collaborations with schools and community organizations in San Diego County (see Letters of Support from San Diego Unified School District [[name]] and SDSU Speech-Language Clinic [[name]]). Permission will be obtained from the school district and local school administrators before conducting recruitment efforts. Following protocol that has successfully been implemented in the past, we will provide teachers and parent groups at area preschools and community centers with information about the project. The study will be announced to prospective caregivers through informational packets (e.g., flyer, SDSU Institutional Review Board-approved parental consent forms, demographic questionnaire, envelope) sent home with the child.

Retention:

Incentives are set at a reasonable rate to cover time and travel, and will be staggered across each participant's enrollment. We will have a part-time clinical research associate devoted to recruitment and retention.

STUDY TIMELINE

	Year 1			Year 2	
	April	May-Aug	Sep-Dec	Jan-Apr	May-Aug
Activity	Recruitment starts (n = 36 participants) Continues through May of Year 2	9 participants for Summer clinic session	9 participants for Fall clinic session	9 participants for Spring clinic session	9 participants for Summer clinic session

PROTECTION OF HUMAN SUBJECTS

1. Risks to Human Subjects

a. Human Subjects Involvement, Characteristics, and Design:

The participants will include 36 English monolingual children between the ages of 4 and 6 years of age with phonological disorder (PD, n = 12), developmental language disorder (DLD, n = 6), or co-occurring PD-DLD (n = 18). The participants will be recruited through schools and community organizations but will not be enrolled in any other speech/language services elsewhere. All participants will have typical intellectual, hearing, social-emotional, and neurological development, per parent report. Both male and female participants will be recruited, as will children from varied racial/ethnic backgrounds.

Participants in all groups will complete a battery of assessment measures. Information gleaned from these measures will be used to further determine eligibility for the proposed study, which include both quantitative and qualitative criteria. Specifically, participating children must pass a binaural hearing screening at 20dB, and score above a standard score of 70 on a test of nonverbal cognition (Leiter-R).¹³⁷

In addition, all PD and PD-DLD participants must exhibit 5 or more sounds in error across three or more speech sound manner classes based on performance on the *Protocol for the Assessment of English Phonotactics* (PEEP),^{82,141} and must score ≤ 1.5 standard deviations below the mean on the *Goldman-Fristoe Test of Articulation 3* (GFTA3).¹³⁵ PD and PD-DLD participants also must exhibit $\leq 20\%$ accuracy on final consonants and clusters independent of tense morphemes, based on performance on the PEEP.¹⁴¹

Moreover, all DLD and PD-DLD participants must score ≤ 1 standard deviation below the mean on the *Preschool Language Scales – Fourth Edition* (PLS-4), a test of expressive and receptive language.¹³⁶ DLD and PD-DLD participants also must exhibit a mean length of utterance (MLU) ≤ 1 standard deviation below the mean for age- and demographic-matched peers, based on a language sample.⁴

